### **9.7.1.3 Final Analysis**

A final study report will be generated after all data collection is complete, or the study is otherwise terminated, including up to 21 months of follow-up for enrolled patients. The final report will encompass all planned analyses, including a description of the complete study population, as described in [Section 9.7.2](#) and in the SAP.

Details and scope for the final analysis will be described in the SAP.

## **9.7.2 Planned Method of Analysis**

### **9.7.2.1 General Considerations**

Descriptive analyses will be performed to gain an understanding of the qualitative and quantitative nature of the data collected and the characteristics of the sample studied. Continuous variables will be reported as mean (and standard deviation), median, minimum, maximum and range where appropriate. Categorical variables will be summarized as number and proportion of the total study population, and by subgroups where appropriate. Analyses will be conducted overall (ever exposed during pregnancy) for erenumab-aooe-exposed and internal comparator cohorts as well as by earliest trimester of erenumab-aooe exposure as applicable. If sufficient numbers are obtained, analyses will also be presented by the subgroups of maternal age, race/ethnicity, prior history of elective or therapeutic pregnancy termination status, prenatal screening result (positive versus negative), prenatal testing status (performed vs not performed), exposure to migraine medications of special interest at baseline, and other important risk factors.

Data analysis for major congenital malformations will be based on first trimester exposure to erenumab-aooe. The primary analysis set will exclude women who have received first trimester prenatal screening, in which either aneuploid disorders or genetic disorders that cause major congenital malformations have been detected, because these disorders are unrelated to medication use. Prematurity-related disorders and transient conditions will also be excluded from the analysis of major congenital malformations.

Patient disposition characteristics including descriptive summaries for enrolled patients, patients in the analysis set, completers and early withdrawals with the reasons for early discontinuations will be provided. In addition, demographic information (eg, age, race/ethnicity, BMI), clinical characteristics including comorbidities and medications, other potential factors that may affect pregnancy outcome, and erenumab-aooe exposure will be described.

All computations and generation of tables, listings, and data for figures will be performed using SAS® version 9.2 or higher (SAS Institute, Cary, NC, USA).

#### **9.7.2.2 Missing or Incomplete Data and Lost to Follow-up**

Key strategies for minimizing missing or incomplete data and lost to follow-up for pregnancy registries include activities for registry awareness, recruitment and retention (of patients and HCP). Complete details of registry awareness, outreach, and retention efforts will be described in a Recruitment and Retention Plan, and may include the following methods to (1) increase awareness of the registry by using multiple approaches aimed towards HCPs and patients, such as websites, social media, print media, and scientific conferences; (2) evaluate awareness of the registry periodically; (3) accept data from multiple sources; (4) minimize the burden on HCPs; (5) ongoing communications with HCPs and patients; (6) possible compensation for HCPs; and (7) minimize the burden on patients. Compensation will be considered for patients and/or HCPs where allowed by local regulations. All activities in this plan will be reviewed on a regular basis. The strategies for these activities are described in more detail in [Section 9.4.4](#).

It is optimal to prevent missing data, to the extent possible, through strategies set forth in the design and conduct of a study. For the current study, we will aim to minimize missing information by the following:

- Ensuring that primary variables of interest are those that are routinely collected as part of real-world clinical care and are available via medical charts, HCP and/or patient reporting, as appropriate
- Collecting only critical data elements (ie, variables aligned with the study objectives) to minimize patient burden
- Including "not applicable", "not done" on the questionnaires that are being completed by patients/HCPs to differentiate these from values that are truly unknown
- Training of CC staff regarding data collection
- Planning an interim analysis(es) to characterize enrollment and loss to follow-up

- Checking for patterns of missingness and addressing any issues with targeted operational strategies
- Implementing direct to patient strategies to facilitate capture of patient-reported information

Should missing data occur, the data will be analyzed as they are recorded in the study eCRFs. However, the amount of missing values for data elements will be reported and will be assessed for the likely impact of missing data on the analysis and the pattern of the missing information. Full details on handling of missing data will be described in detail in the SAP.

### 9.7.2.3 Descriptive Analysis

#### 9.7.2.3.1 Description of Study Enrollment

The selection of the study population per analysis set are described in [Table 5](#).

**Table 5. Analysis Sets**

Analysis Set	Description of Population
Enrolled Set	All women who have signed an informed consent
Full Analysis Set	All women in the Enrolled Set who have any data collected (ie, some study procedures have begun)

#### 9.7.2.3.2 Description of Patient Characteristics

Description of patient characteristics are described in [Section 9.7.2.1](#) (General Considerations).

#### 9.7.2.4 Analysis of the Primary and Secondary Endpoints

The prevalence of major and minor congenital malformations will be calculated using MACDP convention. Major malformations will be analyzed separately from minor malformations, with the primary analysis including only adjudicated major congenital malformations. The total prevalence will be calculated by dividing the number of adjudicated cases of each event (observed in live births, fetal deaths, elective or therapeutic terminations, and at any gestational age) by the total number of pregnancies (excluding spontaneous terminations and ectopic or molar pregnancies). The prevalence at birth will be calculated as number of cases observed in live births and stillbirths divided by the total number of births (stillbirths + live births). Data analysis for major congenital malformations will be based on first trimester exposure to erenumab-aooe.

The prevalence of pregnancy complications, including preeclampsia, pregnancy-induced hypertension, gestational diabetes, placenta previa, and preterm labor, will be summarized by dividing the number of each event by the total number of pregnant women.

The prevalence of spontaneous abortions will be calculated by dividing the number of fetal losses occurring before 20 weeks gestation by the total number of pregnancies.

The prevalence of elective and therapeutic abortion will be estimated similarly as separate outcomes.

Prevalence of preterm birth will be calculated by dividing the number of cases by the total number of births (stillbirths + live births). The prevalence of small-for-gestational-age will be calculated by dividing the number of cases by the total number of live births.

For growth and developmental delays, the prevalence will be calculated as the number of cases divided by the total number of live births.

Prevalence of primary and secondary outcome measures will be presented with 95% CIs for binomial proportion. The analyses summarized in this section will be performed on the erenumab-aooe exposed cohort and the internal comparator cohort consisting of pregnant women with migraine who were not exposed to erenumab-aooe; Characteristics can be matched or stratified in relation to the exposed cohort to control for important covariates such as maternal age (see [Section 9.7.2.5.1](#)).

The maternal, fetal, and infant outcomes of women with migraine exposed to erenumab-aooe will be compared with the internal comparator cohort (see [Section 9.7.2.5.1](#)). Additionally, the observed prevalence of major congenital malformations will be compared to the external comparator cohort(s) (see [Section 9.7.2.5.2](#)).

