### **9.3.2.2 Secondary Outcomes**

#### **9.3.2.2.1 Pregnancy Complications**

##### **9.3.2.2.1.1 Preeclampsia**

Primary preeclampsia will be based on HCP reported diagnosis. It is often defined as the presence of hypertension on 2 occasions at least 4 hours apart after 20 weeks gestation (in a woman with a previously normal blood pressure) and proteinuria; or in the absence of proteinuria, a new-onset hypertension accompanied by 1 of the following conditions: thrombocytopenia, renal insufficiency, impaired liver function, pulmonary edema, or cerebral or visual symptoms ([ACOG, 2019](#)).

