#### **9.5 Study Size**

The sample size was estimated to assess the prevalence of major congenital malformations in infants of women with migraine exposed to erenumab-aooe during pregnancy and associated risk ratio with the internal comparator. Estimated sample size results ranged from 465 to 4,776 in each treatment group (1:1 exposed vs. unexposed internal comparator) to detect risk ratios ranging from 3 to 1.5, respectively ([Table 4](#)). To adequately power an internal comparison of the proportion of major congenital malformation events in the erenumab-aooe exposed, and assuming a 15% drop-out rate and a live birth rate of 62% ([FDA, 2002](#)), 1421 erenumab-aooe exposed pregnant women with migraine would need to be enrolled to observe 749 live births. This sample size would provide 80% power to detect a risk ratio of 2.0 or greater in major congenital malformations relative to an assumed prevalence of 3% in the internal comparator cohort ([CDC, 2008](#)) at a significance level of  $\alpha=0.05$ . Calculations were performed using PASS software version 14.

Given that these numbers assume the prevalence of exposure is sufficient to support recruitment of these numbers, the feasibility of achievement will be re-evaluated at each interim review of the data. The interim analysis planned at year 3 after first patient enrolled and annually thereafter ([Section 9.7.1.1](#)), will include sample size re-estimation, examining the observed prevalence and the risk ratio of major congenital malformations

in the erenumab-aooe exposed compared with the internal comparator, accounting for patient recruitment rates and enrollment projections.

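### Pregnancy complications are divided by all pregnant women, so pregnancies that ended before 20 weeks dilute the preeclampsia risk, and the risk ratio moves with each cohort's share still at risk

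*Protocol*

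**What the plan says.** Protocol Section 9.7.2.4 sets one denominator for five outcomes, "including preeclampsia, pregnancy-induced hypertension, gestational diabetes, placenta previa, and preterm labor". Their prevalence "will be summarized by dividing the number of each event by the total number of pregnant women". Nothing removes pregnancies that ended early. The Full Analysis Set in Table 5 adds no gestational limit, and Section 9.7.2.5.1 carries these frequencies into the risk ratio between the cohorts.

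Section 9.3.2.2.1.1 bases preeclampsia on the healthcare provider's diagnosis and describes its main form as "hypertension on 2 occasions at least 4 hours apart after 20 weeks gestation", with proteinuria. Section 9.3.2.2.2.2 defines spontaneous abortion as a loss before 20 weeks.

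Three other provisions bear on the point:
- Exposure may occur at any time in pregnancy (Section 9.3.1).
- Enrollment before 20 weeks is preferred but not required (Section 9.2.1).
- Results are also presented by earliest trimester of exposure (Section 9.7.2.1).

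**The concern.** A woman whose pregnancy ends at, say, 10 weeks enters the preeclampsia denominator but cannot enter the numerator under the main criterion. Two consequences follow.

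First, the proportion reported for the secondary objective on pregnancy complications lies below the risk faced by a woman whose pregnancy continues. A clinician could easily read it as that risk.

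Second, the two cohorts, or two exposure strata, may contain different shares of early losses and terminations. Their risk ratio for preeclampsia then departs from the ratio among ongoing pregnancies even if exposure has no effect on preeclampsia. Such differences can arise by design. A woman first exposed in the second or third trimester must still have been pregnant at that time, and a woman enrolled late has already passed the period of early loss.

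**Working it through.** **The plan's own figures.** The protocol gives no planning figure for complication risk. The only pregnancy-outcome share that can serve is in Section 9.5, which plans "assuming a 15% drop-out rate and a live birth rate of 62" percent and states that "1421 erenumab-aooe exposed pregnant women with migraine would need to be enrolled to observe 749 live births". With 3% against 6%, two-sided alpha 0.05, 80% power, 1:1 allocation, pooled variance and no continuity correction:

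n = [1.960 × √(2 × 0.045 × 0.955) + 0.842 × √(0.03 × 0.97 + 0.06 × 0.94)]² / 0.03² ≈ 748.4, rounded up to 749 per group.

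Then 749 / (0.85 × 0.62) = 1421.3, and 1421 × 0.85 × 0.62 = 748.9. The plan's figures reproduce, so 62% is the live birth share actually used. (The protocol does not state whether alpha is one- or two-sided; two-sided fits.)

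**Dilution.** Let s be the share of pregnancies that reach the time at risk.

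Reported risk = at-risk risk × s; relative shortfall = 1 − s.

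| s | Basis | Shortfall | 5% at risk is reported as | 10% at risk is reported as |
|---|---|---|---|---|
| 0.62 | planned live birth rate, all other pregnancies ended before 20 weeks | 38% | 3.1% | 6.2% |
| 0.70 | assumed | 30% | 3.5% | 7.0% |
| 0.80 | assumed | 20% | 4.0% | 8.0% |
| 0.90 | assumed | 10% | 4.5% | 9.0% |
| 0.95 | assumed | 5% | 4.75% | 9.5% |

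The 5% and 10% risks are illustrations, not protocol figures. Stillbirths occur at or after 20 weeks and so were at risk. With the 8.0 per 1000 births quoted in Section 9.2.1.1.1, s = 0.62 / (1 − 0.008) = 0.625 and the ceiling becomes 37.5%.

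**Risk ratio.** Reported RR = at-risk RR × (s exposed / s comparator). All pairs below are assumed, because the protocol gives no share by cohort.

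| s exposed | s comparator | Factor on the RR |
|---|---|---|
| equal | equal | 1.00 |
| 0.85 | 0.90 | 0.94 |
| 0.80 | 0.90 | 0.89 |
| 0.62 | 0.70 | 0.89 |
| 0.70 | 0.62 | 1.13 |

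With 0.80 against 0.90, an at-risk RR of 1.5 would be reported as 1.5 × 0.889 = 1.33.

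**By trimester of first exposure.** A pregnancy first exposed in the third trimester has already passed 20 weeks, so s = 1 in that stratum. Against a group with an assumed s of 0.80, the factor is 1 / 0.80 = 1.25 with no drug effect. This part does not depend on any effect of exposure on loss.

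**The case against.** The strongest reply is that the stated ratio is not an error. Section 8.2 asks for the proportion of pregnancy complications in exposed women, and events per enrolled pregnancy is that quantity, with early loss as a competing event. It is low only relative to a different target, the risk among pregnancies that continue. This stands, and is why the crude figure should be kept.

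A reader might infer more than the protocol supports:

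- **That all five complications are understated by 38%.** Only preeclampsia has a 20-week lower limit in the protocol. The definitions of pregnancy-induced hypertension, gestational diabetes and placenta previa give no lower limit, and preterm labor has only an upper one. Even for preeclampsia, the limit belongs to a customary definition, while the working criterion is the provider's diagnosis. Moreover, 38% requires every pregnancy without a live birth to have ended before 20 weeks. Section 9.9.1.3 expects many early losses to be missed because they precede enrollment, which raises s.
- **That the risk ratio is biased, or that erenumab would look protective.** No cohort-specific shares are given. Both cohorts follow the same procedures (Section 9.1) and are recruited from the same clinical centers where feasible (Section 9.9.2). The factor is 1.00 when the shares match.
- **That the section contradicts itself by using births for preterm birth and live births for small-for-gestational-age.** Those denominators follow from outcomes defined among live births. Preterm birth is even divided by live births plus stillbirths, so the section has not adopted a general at-risk rule.

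An at-risk denominator also has a weakness: it conditions on survival to 20 weeks, which follows exposure in many women. If exposure affects loss, that comparison is selected as well.

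Some protection exists. Losses and terminations are reported and compared by cohort, so a difference would be visible. The time-varying Cox analysis in Section 9.7.2.6 covers secondary outcomes, but it depends on sample size and leaves the stated proportion and risk ratio unchanged. The sensitivity analysis by gestational age at enrollment is specified for spontaneous abortion only.

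**Conclusion.** The point holds in a limited form. Section 9.7.2.4 states a rule under which pregnancies that ended before 20 weeks count as free of preeclampsia. Relative to ongoing pregnancies, the shortfall is at most about 38% (37.5% once stillbirths count as at risk) and 5% to 30% over the assumed range of s. The effect on the risk ratio depends on unequal at-risk shares. It is modest in the assumed cohort pairs (factors 0.89 to 1.13), absent if the shares match, and built in for strata defined by later first exposure. For the other four complications the protocol gives no basis for a size.

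This concerns a secondary outcome. It does not touch the primary malformation analysis or the sample size.

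**What to change.** In Section 9.7.2.4, add for preeclampsia, and for any other complication that the sponsor chooses to give a lower gestational limit, the proportion among pregnancies ongoing at 20 completed weeks. Count women who enroll after 20 weeks, since they are eligible and their pregnancies passed that point. Apply the same rule in both cohorts and in the strata by trimester of exposure. In Section 9.7.2.5.1, give the risk ratio on that denominator beside the one on all pregnancies.

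State that the two figures answer different questions, and that both are to be read with each cohort's proportions of spontaneous abortion and termination.

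The cost is a few sentences and one extra column per table. Gestational age at enrollment and at pregnancy outcome is already collected (Appendix F, Tables 1 and 3). The downside to state openly is that the at-risk figure rests on fewer pregnancies and conditions on survival to 20 weeks after exposure, so it should not replace the all-pregnancies figure.

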### 8.2 Secondary

Secondary objectives include the following:

- In women exposed to erenumab-aooe during pregnancy,
  - To estimate the proportion of pregnancy complications
  - To estimate the proportion of spontaneous abortion, still birth, elective termination, and preterm birth
- In infants of women exposed to erenumab-aooe during pregnancy,
  - To estimate the proportion of small-for-gestational age
  - To estimate the proportion of minor congenital malformations
  - To estimate the proportion of postnatal growth and development deficiency through the first year of life
- To compare the proportion of maternal, fetal, and infant outcomes of women with migraine exposed to erenumab-aooe consisting of women with migraine who have not been exposed to erenumab-aooe before or during pregnancy (internal comparator)
- To compare the frequency of major congenital malformations of women with migraine exposed to erenumab-aooe during pregnancy with women representing the prevalence of birth defects in the general population (external comparator)

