**Infant Follow-up (estimated at 12, 26 and 52 weeks of age)**

- Reporter of information (eg, patient, PCP, OB, neurologist [indication specialist], nurse midwife, infant HCP, other)
- Feeding behavior (including breastfeeding)
- Weight
- Length
- Head circumference
- Postnatal growth and development (ie, social/emotional, language/communication, neurocognitive, movement/physical development milestones)
- Breastfeeding status
- Evidence of any new congenital malformations and growth alterations since last follow-up
- Vaccination information
- Patient and infant AEs and SAEs (including event, start date, ongoing or end date, seriousness, severity, relationship to erenumab-aooe, outcome, action taken)

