#### **9.3.2.2.3.4 Postnatal Growth and Development**

Domains of developmental milestones (ie, social/emotional, language/communication, neurocognitive, movement/physical development milestones) by age will be defined by guidelines provided by the CDC ([CDC 2019](#)). As recommended by the CDC, the World Health Organization Growth Charts (suitable for use in the U.S. from birth to 24 months) will be applied for this study, where infant growth measurements will be used to estimate gender-specific weight-for-length, head circumference-for-age, length-for-age, and weight-for-age percentiles. Developmental milestones will be collected as part of routine clinical practice with pediatrician-determined results of infant status (ie, below, above, or at age appropriate achievement) in each of the domains listed above. "Ages and Stages" or similar standardized assessments may be collected for this study if performed as part of routine clinical care – no additional information will be mandated for collection as part of this study.

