## **9.7.2.5 Comparative Analysis**

### **9.7.2.5.1 Internal Comparator Analysis**

Primary and secondary outcome frequencies in the erenumab-aooe exposed cohort will be compared with the internal comparator cohort using the risk ratio (95% CIs). Also, comparisons may be explored using ORs adjusted to relevant covariates as applicable, if a sufficient number of outcomes are available in the subgroups. The covariates of interest may include the maternal age, prior history of elective or therapeutic pregnancy termination status, other migraine treatment exposures (such as preventive migraine treatments other than erenumab-aooe), migraine type, and baseline alcohol status. In

addition, erenumab-aooe exposure specific covariates such as any preconception CGRP mAb exposure (> 5 half-lives prior to LMP) and cumulative duration of exposure to migraine therapies during pregnancy may be explored.

Additionally, to assess the impact of exposure on the primary outcomes the propensity score matching may be explored. Baseline characteristics such as age, migraine history (eg, type of migraine), migraine severity (eg, frequency, duration, treatment burden) and parameters of obstetric history will be explored to match between the erenumab-aooe exposed and internal comparator cohorts.

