**Table 4. Pediatric Follow-up (approximately at infant age 12, 26, and 52 weeks after birth)**

Variable Category	Data Elements	Additional Information
Date of Contact	Date	
Reporter of Information a	Patient	Contact information (any changes); Secondary contact (if available)
	PCP	Contact information (any changes)
	Neurologist (indication specialist)	Contact information (any changes)
	Infant HCP	Contact information (any changes)
	Other (please specify)	Contact information (any changes)
Infant Vaccinations Received since Last Contact	Vaccination and date (with calendar to aid recall)	
Infant Characteristics	Length	Value and percentile score
	Head circumference	Value and percentile score
	Weight	Value and percentile score
	Infant feeding: breastfed, formula, combination breastfed/formula, other (please describe)	Number of weeks exclusively breastfed since birth
	Infant developmental milestones: social/emotional, language/communication, cognitive, movement/physical development milestones	Any identified developmental delays or impairment? If yes, please characterize
	Any new malformation or growth alterations since last visit	Including description and attribution

Footnotes defined on last page of the table

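### Postnatal growth is recorded as values and percentiles at three ages, but the only between-cohort growth comparison the protocol fixes is a proportion of cases; a supportive z-score comparison would be more sensitive to a general shift

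*Protocol*

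**What the plan says.** Section 8.2 sets the growth objective as a proportion: "To estimate the proportion of postnatal growth and development deficiency through the first year of life".

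The data are richer than that. Section 9.2.8 schedules weight, length and head circumference at about 12, 26 and 52 weeks of age. Appendix F, Table 4 asks for "Value and percentile score" for each of the three. Section 9.3.2.2.3.4 adopts the WHO growth charts and states that "infant growth measurements will be used to estimate gender-specific weight-for-length, head circumference-for-age, length-for-age, and weight-for-age percentiles".

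The analysis text reduces these data to a count. Section 9.7.2.4: "For growth and developmental delays, the prevalence will be calculated as the number of cases divided by the total number of live births". Section 9.7.2.5.1: "Primary and secondary outcome frequencies in the erenumab-aooe exposed cohort will be compared with the internal comparator cohort using the risk ratio (95% CIs"; adjusted odds ratios are an option.

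The only provision for continuous data is general and descriptive (section 9.7.2.1): "Continuous variables will be reported as mean (and standard deviation), median, minimum, maximum and range where appropriate". No section sets out a between-cohort difference in mean percentile or z-score, or a model using the three visits together.

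**The concern.** A proportion below a cut responds only to infants who cross the cut. If exposure moved weight, length or head circumference down a little in most infants, few would cross it, and the risk ratio could sit near 1 with a wide interval. A reader could take that as reassurance although the recorded values would have shown the shift. Sections 6 and 9.9.3 expect low enrollment, so there is little information to spare.

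No source cited in the protocol imposes the cut. Section 9.3.2.2.3.4 cites the CDC for milestones and for the choice of growth chart, not for a growth-deficiency threshold. Small-for-gestational-age and preterm birth are different: sections 9.3.2.2.2.5 and 9.3.2.2.3.2 tie them to CDC definitions, and they are outside this point.

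**Working it through.** **Step 1. The plan's own figure.** Inputs from section 9.5: 3% against 6% (risk ratio 2.0), 80% power, alpha 0.05 (two-sided reproduces the figure).

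n = [1.960·√(2·0.045·0.955) + 0.842·√(0.03·0.97 + 0.06·0.94)]² / 0.03² = 748.4, so 749 per group. Enrolment: 749 / (0.85 × 0.62) = 1421. Both match. The plan's claim, "This sample size would provide 80% power to detect a risk ratio of 2.0 or greater in major congenital malformations", concerns malformations only; no power is stated for growth.

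**Step 2. Assumptions for growth.** The protocol gives no cut-off and no expected shift, so these are assumed: normal z-scores with SD 1; a uniform downward shift of d SD; a case defined as below percentile c, with c = 3rd, 5th or 10th; two-sided 5%; 749 infants per group.

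**Step 3. One visit.**
- Mean z-score: power = Φ(d·√(n/2) − 1.96). At d = 0.20: Φ(0.20 × 19.35 − 1.96) = Φ(1.91) = 97%.
- Proportion: p₀ = c and p₁ = Φ(z_c + d), then the two-proportion formula of step 1 solved for power. At c = 5% and d = 0.20: p₁ = Φ(−1.645 + 0.20) = 7.42%; standard errors 0.01247 (null) and 0.01246 (alternative); power = Φ[(0.0242 − 1.96 × 0.01247) / 0.01246] = 49%.

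**Step 4. Three visits.** Because the objective runs through the first year, repeated visits help the proportion as well. Assume a between-visit correlation of 0.7 and count a case if the infant is below the cut at any visit. At d = 0.20 the trivariate normal gives case proportions of 6.5% to 9.6%, 10.3% to 14.6% and 19.0% to 25.3% for the three cuts. The mean of three z-scores has SD √[(1 + 2·0.7)/3] = 0.894, so its power is Φ(0.20/0.894 × 19.35 − 1.96) = Φ(2.37) = 99%.

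**Step 5. Results** (proportion at 3rd / 5th / 10th percentile, against mean):

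| Per group | Shift | One visit | Any of three visits |
|---|---|---|---|
| 749 | 0.15 SD | 23 / 30 / 42% v 83% | 38 / 47 / 59% v 90% |
| 749 | 0.20 SD | 38 / 49 / 66% v 97% | 61 / 72 / 84% v 99% |
| 749 | 0.30 SD | 73 / 85 / 95% v about 100% | 93 / 97 / 99% v about 100% |
| 400 (assumed) | 0.20 SD | 23 / 30 / 41% v 81% | 37 / 46 / 58% v 89% |

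At 0.20 SD and 749 per group the gap is 31 to 59 points at one visit and 15 to 38 points over three. With correlations of 0.6 and 0.8 the three-visit gap also stays below the one-visit gap.

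At one visit and 749 per group, the smallest shift detectable with 80% power is 0.145 SD for the mean, against 0.326, 0.282 and 0.235 SD for the proportion at the three cuts.

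**The case against.** The strongest reply is that the analysis does what the objective asks. Section 8.2 names a proportion, sections 9.7.2.4 and 9.7.2.5.1 deliver one, growth is an unpowered secondary outcome, and an SAP (not at hand) could add a continuous model. This stands in part. Nothing is contradicted, and making the z-score the main comparison would change the stated objective. But the protocol does fix one form of comparison, and an SAP that follows it without addition keeps the loss.

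Second, the dichotomy is partly inferred. No section says that a case comes from cutting a percentile, and the infant follow-up separately records growth alterations, so cases may be reported findings. This stands: the power figures hold only under the percentile-cut assumption.

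Third, the size depends on the form of the effect. This also stands. An effect confined to the lower tail would favour the proportion, and no section says that a shift of 0.15 to 0.20 SD matters clinically.

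Fourth, in a non-randomised registry a method sensitive to small shifts is equally sensitive to small confounding. Section 9.9.1.3 warns of channelling by migraine severity, and section 9.9.1.4 names maternal age and smoking. An unadjusted z-score model would therefore be unsound.

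**Conclusion.** The point holds as a moderate one: the protocol collects continuous, repeated growth data and fixes no between-cohort comparison that uses them as such. Under a uniform shift of 0.15 to 0.20 SD and a percentile cut, the proportion is materially less sensitive, and part of that gap remains when all three visits count. At 0.30 SD with a 10th-percentile cut the difference is small.

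A reader might infer more than this, and the documents do not support it:
- **That most of the power is lost.** No cut, shift or growth power is given. In several of the scenarios above the proportion keeps more than half the power of the mean.
- **That the one-visit gap would widen once repeated visits are used.** Under the any-visit definition it narrows.
- **That growth is analysed only as a proportion.** Section 9.7.2.1 allows descriptive means; what is absent is a fixed comparison of them.

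**What to change.** In sections 9.7.2.4 and 9.7.2.5.1:

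- Keep the deficiency proportion and its risk ratio, as the objective names them.
- Add a supportive between-cohort mean difference with 95% CI in WHO z-scores for weight-for-age, length-for-age, weight-for-length and head circumference-for-age, from a repeated-measures model over the 12-, 26- and 52-week values.
- Adjust that model for confounders the registry already collects, for example maternal age, smoking and migraine severity.
- Name one deciding contrast in advance, for example the 52-week difference, and report the results as estimates without a claim of significance.
- Leave developmental milestones categorical, since section 9.3.2.2.3.4 has them recorded as below, at or above what is expected for age.

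The cost is protocol or SAP wording and one extra model per growth measure, with no new data or visits. The downsides are several supportive estimates to interpret and a mean z-score difference that is less directly clinical than a proportion, which is a further reason to keep the proportion.
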